3.1.1 Stratification, Randomization, and Blinding

Eligible subjects will be randomized in a 1:1:1:1 ratio to one of four cohorts: 5 mg JBT-101 b.i.d., 20 mg JBT-101 q.d., 20 mg JBT-101 b.i.d., or placebo (see Section 3.1, *Description of Study Design*, Table 1). Subjects will be stratified by 7-day average of maximum daily pain NRS score ≤ 6 versus > 6 and Fibromyalgia Symptom Scale Score < 13 versus ≥ 13 at Screening.

To maintain the study blind, JBT-101 and placebo capsules and their packaging will be identical. All subjects will receive b.i.d dosing to maintain blinding to treatment assignment. In general, clinical staff, including the investigators, will be blinded to the treatment assignments until completion of the study. In addition, they will not have access to any mechanistic data, and mechanistic laboratory staff will not have access to any clinical results until completion of the study. The success of blinding will be formally tested using a Treatment Satisfaction Survey that asks each study subject and corresponding site investigator to guess the study group assignment for that subject at the end of active treatment and then comparing these responses to what would be expected by chance.

Unblinding must be approved by the study Medical Monitor unless an immediate life threatening condition has developed and the Medical Monitor is not accessible. The site investigator will notify the protocol chair(s) and the DAIT- Statistical and Clinical Coordinating Center (SACCC) of the unblinding event on the next business day. The emergency unblinding will also be reported to the Data and Safety Monitoring Board (DSMB).

A full account of the event will be recorded, including the date and time of the unblinding, the reason for the decision to unblind, and the name of the individual who made the decision and the names of the Medical Monitor and others who were notified. The reasons for unblinding of a participant's treatment will be included in the final study report.

An individual's treatment assignment will be unblinded if the subject experiences a suspected adverse reaction that is serious and unexpected (see Section 7.2.1, *Adverse Event* and Section 7.2.1.1 *Suspected Adverse Reaction* and Section 7.2.2, *Unexpected Adverse Event*) or other protocol-specific event(s) determined by DAIT/NIAID to warrant unblinding.

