8 STATISTICAL CONSIDERATIONS AND ANALYTICAL PLAN

8.1 Sample Size and Power

A total of approximately 100 eligible subjects (approximately 25 per treatment arm) will participate in the study.

The primary hypothesis will be tested using the 3 degree of freedom (df) contrast comparing the difference in predicted means from Day 1 to Day 84 for each JBT-101 cohort versus placebo, where estimates will be derived from a random regression model (See Section 8.3.2.1, *Primary Efficacy Analysis*). The method of Stroup (1999) [123] was used to estimate power and sample size. To apply the method, we made reasonable assumptions about (1) the covariance matrix for the random effects and the residual variance, and (2) mean changes over time for each treatment group.

Subjects who complete the study will have approximately 84 NRS scores assessed daily. To derive the within-subject covariance matrix, we need the within-subject correlation matrix and the standard deviation. We assume the daily assessments have an AR(1) within-subject correlation structure, which seems reasonable based on preliminary data on 24 subjects assessed on days 1, 14, and 28 [101]. Based on this preliminary data, the correlation coefficient for assessments 1 day apart is very high (estimated as 0.9775). The standard deviation (SD) of the NRS is assumed to be the same for each day and likely to be on the range from 1.3 to 1.6. The range is based on a study by Farrar (2001) [124] that examined data from 10 clinical trials including 2724 patients with a variety of conditions characterized by chronic pain who had baseline pain of \geq 4 on the NRS. The study suggests that patient's perceptions of pain and improvement is similar and consistent across disease indications. Results of this study influenced the recommendations on clinical importance of treatment effects on pain in clinical trials (IMMPACT) group [125].

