The covariance matrix for the 84 repeated NRS measures can be derived assuming an AR(1) correlation matrix (r=0.9775 for a 1 day interval) and a choice of SD; we considered the two extremes in SD = 1.3 and 1.6, as well as the pooled estimate (1.43) across the 10 studies in [124]. The next step was to derive the covariance matrix for the random effects in the random regression model (i.e. the subject-level intercepts and slopes). To this end, we simulated day 0 to 84 data for 10,000 subjects, fit the model with fixed and random subject-level intercepts and slopes, and used the output covariance estimates as parameters for power/ sample size computation. Covariance parameters are displayed in Table 5.

	Variance (intercept)	Variance (1-day slope)	Covariance (intercept, slope)	Residual
Pooled (daily NRS SD=1.43)	2.35	0.00063	-0.027	0.49
Best case (daily NRS SD=1.3)	1.93	0.00053	-0.023	0.41
Worst Case (daily NRS SD=1.6)	2.96	0.00081	-0.034	0.62

We considered several scenarios for mean changes over time. The IMMPACT group suggests that on average decrease of 2 points (~30% improvement on average) on the NRS scale is consistent with clinically important improvement from the perspective of an individual patient, but they did not make a recommendation for clinically relevant mean decrease in NRS for a treatment group relative to placebo [125]. Although a mean decrease of 2 points on the NRS for a treatment group would certainly be important clinically, a decrease of a smaller magnitude might also include a substantial number of individual subjects who showed improvement of at least 2 points. As such, we considered mean decreases, d, ranging from 1.5 to 2.0 points over 84 days and assumed no change for placebo. For each value of d, we present power/sample size calculations for 2 scenarios. In Scenario 1, the mean decrease of d is achieved in 1 of the JBT-101 treatment groups. The other 2 JBT-101 groups show mean decreases of 0.5d and 0.25d. In Scenario 2, two of the JBT-101 treatment groups achieve a mean decrease of d, and the third shows a decrease of 0.25d. These scenarios are summarized in Table 6. We also considered a 3rd scenario where all 3 treatment groups achieved a mean decrease of d, but power estimates were nearly identical to Scenario 2, and hence, results are not shown.

Table 0. Treatment Effect Scenarios								
	Scenario 1	Scenario 2						
Placebo	0	0						
JBT-101 group 1	-0.25d	-0.25d						
JBT-101 group 2	-0.5d	-d						

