8.3 Description of the Analyses

- All data will be provided in data listings sorted by treatment groups, subject number, and visit.
- Summary data will be presented in tabular format by treatment groups.

- Categorical data will be summarized by the number and percentage of subjects in each category.
- Continuous data will be summarized by descriptive statistics including N, mean, standard deviation, median, and range.
- All percentages will be rounded to one decimal place.
- Differences between groups will be calculated as active placebo and change from baseline (ΔNRS) will be calculated as follow-up visit – baseline.
- The baseline measure will be defined as the last non-missing measure prior to initiation of study product. It is expected that baseline values for efficacy assessments will be measured at Visit 1 (Day 1).
- P-values will be assessed at a 2-sided alpha = 0.05 level for the primary efficacy analysis.
- Secondary analyses are exploratory and intended to deepen our understanding of risks and benefits, to refine hypotheses, and to obtain information from which to design, select doses, and power future pivotal studies. P-values will be presented for secondary efficacy analyses. No adjustments for multiple comparisons are planned for secondary analyses.

8.3.1 **Subject Disposition**

The disposition of all subjects over the course of the trial will be summarized by cohort and overall. The number and percent of subjects in each analysis population (mITT, PP, safety, and PK) will be displayed. In addition, the presentation will include the number of subjects who completed the study, the number who withdrew prematurely from the study, as well as the reason for withdrawal. In addition, the number of subjects who continued treatment to Visit 5 (Day 85) and who discontinued treatment early will also be summarized along with reasons for discontinuation.

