8.3.2 Efficacy Analysis

8.3.2.1 Primary Efficacy Analysis

The primary hypothesis for this study is that JBT-101 treatment will result in improvement in the maximum daily pain NRS scores in SLE patients with active musculoskeletal disease. The null hypothesis to be tested is:

H0: Linear trends from Day 1 to Day 84 are equivalent for each JBT-101 cohort and placebo. HA: Linear trends from Day 1 to Day 84 are not equivalent across groups.

In addition, pairwise comparisons of each JBT-101 cohort versus placebo are of key interest.

For the primary analysis, the maximum daily pain NRS scores from Day 1 through end of treatment (typically Day 84) will be modeled using a random regression approach. The fixed

effects model will include treatment group, time, time², time- and time² by treatment group interactions, as well as the Screening 7-day average maximum daily pain NRS as a covariate. Within-subject random effects for intercept and slopes for time and time² will be fit using an unstructured covariance matrix assuming the same structure for all treatment groups. In the event of convergence problems, the covariance structure will be simplified by dropping the random effect for time². The primary hypothesis will be tested using the 3 degrees of freedom contrast comparing the difference in predicted means ($\hat{\mu}$) from Day 1 to Day 84 for each JBT-101 group versus placebo. That is, ($\hat{\mu}_{84} - \hat{\mu}_1$)_{cohort i}- ($\hat{\mu}_{84} - \hat{\mu}_1$)_{placebo} = 0 for i=1 to 3.

NRS data up to the day of last dose of study treatment will be included in the analysis for all subjects in the mITT population. Any NRS data entered into the IVRS after discontinuation of study treatment or entered on days when narcotic analgesics were taken will be excluded. If the 3 df test is significant, Dunnett's tests for 1 df pairwise comparisons with placebo are planned. If the 3 df test is not statistically significant, confidence intervals for the 1df pairwise comparisons with placebo will still be presented, but this information will be used for hypothesis generation and planning of future studies.

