8.8 Multiple Comparisons and Multiplicity

The primary analysis for the efficacy of JBT-101 compares the individual trajectories of the 4 cohorts over time. Section 8.3.2 describes the use of Dunnett's test for multiple comparisons against the placebo group. The secondary efficacy analyses will evaluate trends for efficacy, with p-values and confidence intervals presented as descriptive measures of strength of

evidence rather than formal statistical inference. Therefore, no additional multiplicity adjustments are needed for this study.

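### Dunnett's tests after a significant 3 df test are valid but conservative; a closed step-down procedure behind the same gate would recover about 2 to 7 points of power per effective dose

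*Protocol*

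**What the plan says.** Section 8.3.2.1 defines the primary test: "The primary hypothesis will be tested using the 3 degrees of freedom contrast comparing the difference in predicted means" between Day 1 and Day 84, each dose group against placebo. Section 8.3 sets the level: "P-values will be assessed at a 2-sided alpha = 0.05 level for the primary efficacy analysis".

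The dose comparisons have a stated role in the same section: "In addition, pairwise comparisons of each JBT-101 cohort versus placebo are of key interest". They are tested only behind the primary test: "If the 3 df test is significant, Dunnett's tests for 1 df pairwise comparisons with placebo are planned". If the 3 df test is not significant, pairwise confidence intervals are still shown, but for hypothesis generation and planning only.

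Section 8.8 refers back to this as the multiplicity method: "Section 8.3.2 describes the use of Dunnett's test for multiple comparisons against the placebo group". Neither section says whether the test is single-step or step-down. Without a qualifier, the usual meaning is the single-step test, with one critical value for all three comparisons.

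**The concern.** Single-step Dunnett is built to hold the familywise error at 5% from a standing start, with no earlier test. Here it starts only after a global test has rejected at 5%. By the closure principle the global test already deals with the case in which no dose works, so the later steps need protect only against the cases in which some doses work and others do not. Those cases involve at most two null doses, and the three-comparison critical value is more than they need.

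What is at stake is power for the dose claims. The arms are small, the protocol calls these comparisons of key interest, and section 1.6 expects the data to support the choice of dose and regimen. Section 8.1 gives power for the 3 df test only, so the power of the dose comparisons is not visible in the plan.

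**Working it through.** **Inputs.** Two-sided alpha of 0.05 (8.3). Equal allocation (3.1.1) and 25 per group (8.1). Pooled row of Table 5: variance of the 1-day slope 0.00063, residual 0.49. Table 6 with placebo at 0: Scenario 1 has doses at 0.25d, 0.5d and d; Scenario 2 has 0.25d, d and d. As in section 8.1, the model is a linear random-slope model with complete data.

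**Variance of the Day 1 to Day 84 change, per subject.**
- Sxx = 84(84² − 1)/12 = 49,385.
- Variance = 83² × (0.00063 + 0.49/49,385) = 6,889 × 0.00063992 = 4.408, so SD = 2.10.
- Standard error of a dose-placebo difference = √(2 × 4.408/25) = 0.594.

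**Reproducing the protocol's power.** The noncentrality is 25 × Σ(μ − mean)²/4.408, with 3 and 96 df.
- Scenario 2, d = 1.6: means 0, 0.4, 1.6, 1.6; sum of squares 2.04; noncentrality 11.57; power 80.8%. Section 8.1 says it exceeds 80%.
- Scenario 1, d = 1.9: means 0, 0.475, 0.95, 1.9; sum of squares 1.974; noncentrality 11.20; power 79.4%. Section 8.1 gives 1.9 as the effect needed for 80%.

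The model therefore agrees with the plan's own calculation.

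**Critical values of |t| at 96 df (simulated).** Three-comparison Dunnett 2.39, two-comparison Dunnett 2.25, unadjusted 1.98. Multiplied by 0.594, the observed difference a dose must exceed is about 1.42, 1.33 and 1.18 points.

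**The two procedures.**
- As written: the 3 df test rejects, and |t| for the dose exceeds 2.39.
- Closed: the 3 df test rejects; for each of the two pairs containing the dose, the larger |t| exceeds 2.25; and the dose's own |t| exceeds 1.98.

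A dose that passes the first rule has |t| above 2.39 and so passes every step of the second. The closed procedure therefore never loses a rejection that the written plan makes.

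**Error rates (simulation).**

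| Configuration | As written | Closed |
|---|---|---|
| No dose works: any false dose claim | 3.1% | 3.5% |
| One very effective dose, two null | about 3.5% | 5.0% |
| Two very effective doses, one null | 1.9% | 5.0% |

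**Power, 25 per group, d = 1.6 (simulation).**

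| Configuration | As written | Closed |
|---|---|---|
| Scenario 2, each dose at d | 60% | 64% |
| Scenario 2, any dose | 74.3% | 76.4% |
| Scenario 1, dose at d | 56% | 58% |
| All three doses at d, each dose | 60% | 67% |
| All three doses at d, any dose | 77.9% | 78.0% |

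**Sensitivity.** With an 84-day rather than 83-day span, Scenario 2 at d = 1.6 gives 59.2% against 63.2% per effective dose. Scenario 1 at d = 1.9 gives 73.2% against 74.8% for the top dose. The direction is the same with the best-case and worst-case rows of Table 5 and with 22 to 30 per group.

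**The case against.** **Single-step is an inference.** The protocol says only Dunnett's test, and section 8.10 leaves the detailed description to a statistical analysis plan that is not at hand. If that plan specifies a step-down form, the improvement is largely in place. This stands as a limit. But section 8.3.2.1 does fix the sequence of 3 df test and then Dunnett, and the unqualified name is normally read as single-step.

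**Nothing is invalid.** Familywise error stays at or below 5%, and choosing a conservative valid method is permissible. This stands, and it sets the weight of the point.

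**The gate is not redundant.** A reader might infer that, since Dunnett's test controls error alone, the 3 df gate buys nothing and ungated Dunnett tests would be the better plan. The protocol does not support that. The 3 df contrast is the test of the stated primary hypothesis and the basis of the power calculation. If it and ungated Dunnett tests could each yield a claim, the chance of a false claim when no dose works would be 5.0% + 5.0% − 3.1% = 6.9%. The gate holds this at 5%, and removing it would change the primary decision rule.

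**The gain is modest and has a price.** It is about 2 points for a lone effective dose and reaches 7 only if all three doses work. Single-step Dunnett also gives simultaneous intervals that agree with its own decisions, which is useful in a small trial that reports pairwise intervals for planning. Dose choice will also draw on the dose-response model and pooled contrast in section 8.3.2.2, and section 8.1 accepts low power for a single effective dose. All of this stands. It argues for a low priority, not against the change.

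**Conclusion.** The point holds as a cheap improvement. On the ordinary reading, the written sequence is valid but applies a stricter critical value to each dose than 5% familywise control needs once the 3 df test has rejected. The loss per effective dose at d = 1.6 is about 4 points in Scenario 2, 2 points for the top dose in Scenario 1, and 7 points if all three doses work. The chance of declaring at least one dose changes little: about 2 points in Scenario 2 and almost nothing if all three work.

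The conclusion rests on the single-step reading and, for its size, on complete data, 25 per group and the pooled covariance of Table 5. It does not mean that the plan inflates error, that the gate should go, or that the 3 df power in section 8.1 is wrong. That power does, however, describe the global test only: in Scenario 2 at d = 1.6 it is just over 80%, while under the written plan the chance of declaring any dose is about 74%.

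**What to change.** Keep the 3 df test as the primary test and as the gate. In sections 8.3.2.1 and 8.8, name the procedure that follows it as a closed (step-down) one: a dose is declared different from placebo if the 3 df test, both two-dose Dunnett tests that contain that dose (critical value about 2.25) and its own t test (about 1.98) all reject at two-sided 5%. If a step-down form was already intended, saying so is the whole change.

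Do not replace Dunnett by unadjusted t tests after the gate. With one very effective dose and two null doses, that gives a familywise error of about 9.0%.

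The cost is one paragraph, with no additional subjects and no change to the primary hypothesis. Simultaneous confidence intervals will no longer correspond exactly to the step-down decisions, and the text should say so.

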8.3.2.2 Secondary Efficacy Analyses

Secondary analyses of the longitudinally assessed maximum daily pain NRS scores will include:

- A 1 df contrast to compare placebo versus the average across all treated groups
- Analyses to modify the primary analysis model by replacing treatment group with JBT-101 dose, so that dose response may be evaluated
- Modification of the primary random regression model to include interaction terms to evaluate the impact of the Screening 7-day average maximum daily pain NRS on trends over time
- Analyses analogous to the primary analyses using % change in NRS from baseline (i.e. where baseline is the Screening 7-day average maximum daily pain NRS) as the outcome variable
- Evaluation of persistence in trends after treatment is stopped by including data after day 84 in a new random regression model where slopes are allowed to change after this point

The 7-day average of maximum daily pain NRS scores prior to Visits 1 (Day 1), 3 (Day 29), 4 (Day 57), 5 (Day 85), and 6 (Day 113) will be used to identify responders whose averages improve by 30% (or 50%, 75% or 100%) over Visit 1 (Day 1) and to evaluate ordinal changes in pain categories (major improvement, improvement, no change, worsening) from Visit 1 (Day 1) to subsequent visits. Relationships between treatment group and each categorical outcome will be evaluated using contingency table analyses. Generalized linear models that account for the correlation structure of the data may be used to further explore any trends that might be suggested by the stratified analyses.

Analyses plans for other categorical secondary endpoints (e.g. presence/absence of arthritis on the SELENA SLEDAI or BILAG scores for the musculoskeletal domain) will be analogous to those noted in the previous paragraph. Generally, mixed models will be used to evaluate disease activity or patient-reported secondary endpoints that are indices or scores assessed at Visits 1 - 5 (Days 1 - 85). Models will be used to compare trajectories and changes in the secondary endpoints over time among the individual JBT-101 groups (Cohort 1, Cohort 2, and Cohort 3) and placebo (Cohort 4). Data transformations will be considered, as appropriate. Larger models may be constructed for these comparisons with consideration of additional covariates that are found to differ between the treatment groups. Covariates may include, but are not limited to: 7-day average of the maximum daily pain NRS score at Visit 1 (Day 1), Fibromyalgia Symptom Score at Visit 1 (Day 1), gender, age, disease duration, and severity.

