8.5 Other Statistical Considerations

8.6 Covariates

No specific adjustments for covariates are planned for this study.

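### Covariates for the secondary score models may be chosen because the arms differ on them; the stratification factors and the endpoint's baseline should be fixed in advance, and section 8.6 corrected

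*Protocol*

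**What the plan says.** Section 8.3.2.2 plans mixed models for disease-activity and patient-reported "secondary endpoints that are indices or scores assessed at Visits 1 - 5 (Days 1 - 85"). They compare the three active arms and placebo on trajectories and on changes. No covariate set is fixed for them. The section then allows larger models to be built, with "consideration of additional covariates that are found to differ between the treatment groups". The candidate list is open-ended. It names the Visit 1 seven-day average of the pain score, followed by "Fibromyalgia Symptom Score at Visit 1 (Day 1), gender, age, disease duration, and severity".

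The first two candidates are the stratification variables measured again at Visit 1. Section 3.1.1 reads "Subjects will be stratified by 7-day average of maximum daily pain NRS score" (cut at 6) and adds the Fibromyalgia Symptom Scale (cut at 13), both at Screening.

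Section 8.6 says "No specific adjustments for covariates are planned for this study". Section 8.3.2.1, however, puts the Screening seven-day average pain score into the primary model as a covariate.

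Sections 8.3 and 8.8 describe the secondary analyses as exploratory and their p-values as descriptive. Section 8.3 also says that they serve to design, choose doses for and power later pivotal trials.

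**The concern.** With randomized, blinded 1:1:1:1 allocation, any baseline difference between arms is due to chance. A rule that adds a covariate because the arms differ on it looks at the wrong property. A covariate earns its place by predicting the outcome, whether or not it happens to be balanced. The rule also sets no threshold for what counts as differing, and the list can be extended, so the model can be settled only after the baseline data are seen.

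The rule works against the protocol's own design. Section 1.6.1 stratifies on fibromyalgia to deal with its effect on pain. Stratification reduces imbalance on the two chosen variables, so they become the candidates least likely to be adjusted for. Section 8.1 recognises that a baseline covariate can cut residual variance and raise power, but the benefit is secured only where the primary model's Screening pain score is carried over.

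With about 25 subjects per arm, precision is scarce, and these estimates are meant to inform the choice of dose. Section 8.6, read as written, also denies the covariate that section 8.3.2.1 fixes.

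**Working it through.** **The plan's own figures.** The protocol gives no number for the secondary models. The nearest is the primary power: above 80% at d = 1.6, Scenario 2, pooled SD, 25 per group. It reproduces:
- Sxx = 84(84² − 1)/12 = 49,385.
- Variance of the 84-day change = 84² × (0.00063 + 0.49/49,385) = 4.515.
- Arm means 0, −0.4, −1.6, −1.6 have squared deviations summing to 2.04, so λ = 25 × 2.04/4.515 = 11.3.
- Power is 0.798 with 96 denominator df and 0.815 with large df.

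That figure is not in dispute, and section 8.1 says it omits the covariate's contribution.

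**How often chance triggers the rule.** The protocol sets no threshold, so p < 0.05 is an assumption. One covariate left to simple randomization differs at that level in 5% of trials. Taking candidates as independent:
- all six: 1 − 0.95⁶ = 26.5% (at p < 0.10, 1 − 0.90⁶ = 46.9%);
- the four not used for stratification: 1 − 0.95⁴ = 18.5% (at p < 0.10, 34.4%).

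These are chances that some covariate is picked up. They are not error rates.

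**Cost for a prognostic covariate that is not otherwise in the model.** Simulation: four arms of 25, 20,000 runs per setting, standardised outcome, one covariate with correlation ρ to the outcome (assumed; the protocol gives none), one active arm differing from placebo by 0.8 SD. Under the imbalance rule the model adjusts only if the 3 df baseline test has p < 0.05.

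| ρ | Power, unadjusted | Power, imbalance rule | Power, always adjusted |
|---|---|---|---|
| 0.3 | 0.80 | 0.80 | 0.83 |
| 0.5 | 0.80 | 0.81 | 0.90 |
| 0.6 | 0.80 | 0.81 | 0.94 |
| 0.7 | 0.80 | 0.81 | 0.97 |

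The rule adjusted in about 5% of runs. At ρ = 0.5 the standard error of the difference was 0.24 SD when always adjusted, 0.27 under the rule and 0.28 unadjusted. With no true difference, rejection was 0.043-0.049 under the rule and 0.049-0.052 when always adjusted. The covariate was not stratified in the simulation; a stratified one would trigger the rule less often.

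**Cost for the endpoint's own baseline.** Here the unadjusted comparison above is the wrong reference, because Visit 1 is already among the modelled responses and the models compare changes. With equal variances σ² at Visit 1 and one follow-up visit:
- change from baseline: 2σ²(1 − ρ);
- baseline as covariate: σ²(1 − ρ²);
- ratio (1 + ρ)/2, so the saving is (1 − ρ)/2.

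At ρ = 0.5 the saving is 1 − 0.75/1.00 = 25%. At ρ = 0.7 it is 1 − 0.51/0.60 = 15%. If the model constrains Visit 1 means to be equal across arms, the gain is already made and the saving is about zero.

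**Sections side by side.** Section 8.3.2.1 fixes one covariate, section 8.3.2.2 allows others, and section 8.6 says that no specific adjustment is planned. Section 8.6 cannot stand as written beside section 8.3.2.1.

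**The case against.** The strongest reply is that the sentence is permissive, the analyses are exploratory, section 1.6 does not expect secondary changes to reach significance, and section 8.10 defers detail to a statistical analysis plan that is not shown. All of that is true, and it limits the stakes. It does not answer the point, because the protocol does more than leave the covariates open: it names a criterion, and the criterion is a poor one. The conflict between sections 8.6 and 8.3.2.1 also lies within the protocol.

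A reader might infer more than the document supports:
- **That the strata and baseline are left out.** They are not. Both stratification variables are candidates, and Visit 1 sits in the modelled response. The secondary pain-score models that modify the primary model build on its Screening covariate. The point concerns only the score and index models.
- **That type I error is inflated.** The simulation shows none for a single covariate, and the primary test is untouched.
- **That adjusting for the endpoint's baseline would cut variance by ρ², or 25-49% at ρ = 0.5-0.7.** That compares with an unadjusted follow-up mean, which is not what these models estimate.
- **That 26% or 47% is a false-positive rate.** Both figures rest on an assumed threshold and on independence, and they treat the stratified variables as if they varied freely.

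**Conclusion.** The concern holds as a matter of precision and prespecification. Selecting covariates by observed imbalance follows chance, ignores prognosis, and tends to leave out the two variables the design treats as important. For a prognostic covariate not otherwise in the model, the rule recovers almost none of the available gain: at 25 per arm, power is 0.81 against 0.90 at an assumed correlation of 0.5, and 0.80 against 0.83 at 0.3. For the endpoint's own baseline the loss is 15-25% of variance at assumed correlations of 0.7-0.5 against a change contrast, and may be nil depending on how Visit 1 is parameterised. The correlations and the p < 0.05 trigger are assumptions. Because the larger models are optional and the analyses exploratory, this is an improvement worth making at almost no cost; it does not threaten the trial's main conclusion. The statement in section 8.6 needs correcting in any case.

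**What to change.** Replace the sentence on larger models and its candidate list in section 8.3.2.2 with:

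> Mixed models for secondary scores will include the two randomization stratification factors (Screening 7-day average pain NRS ≤ 6 vs > 6; Fibromyalgia Symptom Scale < 13 vs ≥ 13) and will account for the endpoint's Visit 1 value, either as a covariate with only post-baseline visits as response or by constraining Visit 1 means to be equal across arms. Covariates will not be selected by observed imbalance, except in labelled sensitivity analyses.

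Giving the two options for Visit 1 keeps the same measurement from appearing both as response and as covariate. Categorical endpoints analysed by contingency table are outside this sentence.

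Reword section 8.6 to state the Screening pain covariate of the primary model and refer to the revised section 8.3.2.2. The cost is a few sentences, to be carried into the statistical analysis plan before database lock. All the variables are already collected.
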